8 STUDY POPULATION

Unless otherwise noted, the ITT population will be used for listings of the study population. ITT and PP populations will be used for summaries of the study population.

8.1 Analysis Populations

An analysis population listing will be provided for all enrolled subjects. This listing will include, for each population detailed in Section 5, whether or not the subject was included in the population and the reason for being excluded from the population. Number and percentage of subjects in each analysis population (ITT, PP, and Safety) will be summarised by treatment arm and overall (both treatment arms combined) for the Randomized population. The denominators for calculating the percentages will be based on the subjects of the Randomized population for the treatment arm summarised.

8.2 Subject Disposition

Subject disposition will be presented for all screened subjects. Number and percentage of subjects who enrol, complete the study, prematurely discontinue from the study, and reasons for study discontinuation will be summarised by treatment arm and overall. The denominator for calculating percentages will be based on the number of screened subjects.

8.3 Inclusion/Exclusion Criteria

Inclusion and exclusion criteria failures will be included in a data listing for the ITT population.

8.4 Protocol Deviations

Major deviations, for the purpose of the statistical analyses, are defined to be those deviations that could potentially bias either efficacy or safety conclusions of the study. Subjects associated with major protocol deviations will be identified and flagged prior to freezing (or, locking) the database at each of the two planned database freeze (or, lock) timepoints (interim analysis freeze/lock and end-of-study freeze/lock).

Major protocol deviations include, but are not limited to, the following categories:

- Subjects that received at least one dose of a study drug and who did not satisfy major inclusion/exclusion criteria.
- Subjects meeting conditions for withdrawal who were not withdrawn.
- Subjects that received a prohibited concomitant medication.
- Subjects that had at least one major required protocol procedure not being performed. Examples of major required protocol procedures include missing haemoglobin results at baseline and/or at Week 12.
- Subjects that received the opposite study drug treatment than the one to which they were randomized.
- Repeated non-compliance in self-administration of ferric maltol study drug, where non-compliance is less than 80% or greater than 120% of expected administration of study drug.
- Other relevant deviations, to be judged on an individual basis.

Protocol deviations will be summarised with frequency distributions (counts and percentages) by treatment arm, category, and deviation type (minor and major) for the ITT population. The denominators for calculating percentages will be based on the number of subjects in the analysis population for each treatment arm and overall.

Protocol deviations will be provided within a data listing by subject.

8.5 Demographic and Other Baseline Characteristics

The demographics listing will include year of birth, age, gender, ethnicity (Hispanic/Latino or non-Hispanic/Latino), race (American Indian/Alaskan Native, Asian, Black/African American, Native American/Pacific Islander, White, Other), and baseline Hb.

The listing of reproductive status will include fertility status (sterile, post-menopausal, potentially fertile), method of birth control (barrier method with spermicide, oral contraceptives, depot contraceptives [implants/injectables], injectables, intrauterine device, complete sexual abstinence, vasectomized partner,

none, other), date of last menstrual cycle, and whether it has been more than one year since the last menstrual cycle.

The listing of randomization will include the stratification levels for IBD subgroup (UC or CD) and screening Hb (< 10g/dL or ≥ 10g/dL for Females; < 11g/dL or ≥ 11g/dL for Males), the randomization date/time, assigned (planned) treatment arm, and the actual treatment corresponding to the study drug received.

The listing of IBD status will include date (month and year) of IBD diagnosis, date (month and year) for each of the last 3 flares of IBD preceding randomization, and IBD subgroup.

Demographic and baseline characteristics will be summarised using descriptive statistics by treatment arm and overall for the ITT and PP populations. The summary will present: each of the variables included in the demographics listing, with the exception of year of birth; fertility status, summarised separately for males and females; and, the stratification levels used in randomization. Subjects who report more than one racial category will be summarised in a separate derived race level labelled as "Multiple".

8.6 Prior and Concomitant Medications

Prior and concomitant medications, including: all prescription iron replacement therapies taken in the last 12 months prior to screening; all oral ferrous treatment history prior to screening; and, all IV Iron treatment history prior to screening will be coded with the World Health Organization (WHO) drug dictionary. Prior and concomitant medications will be separately summarised with descriptive statistics by drug Anatomical Therapeutic Chemical (ATC) Classification System (level one), generic name, and treatment arm for safety population. Data listings will be included that show all medications by generic name and verbatim name.

8.7 Medical History

A comprehensive data listing of all medical histories and ongoing conditions (including start and stop dates and status at end of study) – for the immediate 5 years preceding randomization – will be included. Medical history codes will be summarised for each treatment arm and overall for both ITT and PP populations.

8.8 Subject Progress and Unscheduled Visits

Progression for each scheduled visit will be displayed in a listing by subject. An unscheduled visit listing will include the date of each visit and a description of the assessments performed at the visit.

8.9 Study Drug Disposition

The duration of exposure (days) to study drug will be summarised by treatment arm using descriptive statistics for the Safety population. Duration of exposure will

be calculated as the difference between the last dose date of study drug and the first dose date of study drug plus 1 day. Administration dates of IV Iron will be provided in a data listing by subject, for those subjects randomized to the IV Iron treatment arm.

Compliance with ferric maltol will be assessed at each visit for which the study drug is returned by the subject, and also assessed over the entire Treatment Period. Compliance will be evaluated by comparing the expected number of capsules of ferric maltol administered – based on the total number of treatment days between visits and within the entire treatment period – with the actual number of capsules of ferric maltol taken. If the return date is missing for a particular visit, then compliance will be missing for that visit. Compliance with ferric maltol will be calculated for subjects of the Safety population who are randomized to the ferric maltol treatment arm. Compliance values that are less than 0% will be set to 0%. Summaries of compliance will be presented using descriptive statistics for subjects of the Safety population who are randomized to the ferric maltol treatment arm. A data listing of treatment compliance will be provided by subject, for those subjects of the Safety population who are randomized to the ferric maltol treatment arm.

Compliance will be calculated as follows and expressed by a percentage:

$$\text{Compliance} = (\# \text{caps disp} - \# \text{caps ret}) / (\# \text{caps exp to be administered}),$$

where # = number of, caps = capsules, disp = dispensed, ret = returned, exp = expected.

9 EFFICACY ANALYSES

The ITT and PP populations will be used for summaries and analyses of all efficacy endpoints described below.

In addition to the tables described in the sections below, data for efficacy variables will be provided in data listings by subject.

9.1 Primary Efficacy Analyses

9.1.1 Primary Analysis

Haemoglobin (Hb) concentration will be collected at screening (Visit 1), pre-randomization at Visit 2 (baseline assessment), and at each visit over the Treatment Period. Hb concentration (Observed Cases [OC]) will be summarised for the ITT and PP populations using descriptive statistics by visit for each treatment arm and overall. A scatterplot of Hb concentrations (OC) at Week 12 versus baseline will be presented by treatment arm for the ITT and PP populations.

A dichotomous variable, representing response status in the degree to which Hb increases relative to baseline, will be calculated for each visit over the Treatment Period. Those subjects with at least 2g/dL increase in Hb from baseline or who

have normalization of Hb (>12.0 g/dL for women, >13.0 g/dL for men) will be classified as "Hb responders".

The null hypothesis for the primary efficacy endpoint analysis is that the proportion of Hb responders at Week 12 in the ferric maltol treatment arm is at least 20% lower than the proportion of Hb responders at Week 12 in the IV Iron treatment arm (i.e., ferric maltol is inferior to IV Iron for rate of Hb response at Week 12). The alternative hypothesis is that the proportion of Hb responders at Week 12 in the ferric maltol treatment arm is not worse than 20% lower than the proportion of Hb responders at Week 12 in the IV Iron treatment arm (i.e., ferric maltol is non-inferior to IV Iron for rate of Hb response at Week 12).

The proportion of Hb responders at Week 12 will be compared between the two treatment arms, by calculating a 2-sided confidence interval for difference in the proportions of Hb responders (risk difference) between the two treatment arms and comparing the lower confidence limit of this CI to the pre-specified non-inferiority margin. The CI will be calculated using the Delta Method approach [1] based on a logistic regression model, adjusted for treatment arm, baseline Hb (below the observed median or at least the observed median), and IBD subgroup (UC or CD).

Note that missing values for the Hb responder status at Week 12 primary efficacy analysis will be imputed using a multiple imputation approach for ITT population. BOCF will be used in the case of missing baseline data to use the screening value. Missing values of Hb concentration at Week 12 will be imputed using the SAS[®] procedure MI. This will generate 20 complete datasets containing imputed values of Hb concentration at Week 12 for those missing in the original dataset. Variables considered helpful in guiding this imputation are baseline (Visit 2) Hb concentration and treatment arm. The code for implementing the SAS[®] procedure MI is:

```
PROC MI DATA = <dataset _name> NIMPUTE = 20 SEED = <seed> OUT = MI_out;  
  VAR baselineHb TreatmentArm Week12Hb;  
  EM MAXITER = 10000;  
RUN;
```

Each model, corresponding to a given endpoint analysis, will be fitted against each of the imputed datasets. The SAS[®] procedure MIANALYZE will then be used to combine the individual analysis results for the given endpoint into one result.

The null hypothesis for the primary efficacy analysis will be rejected (i.e., ferric maltol will be deemed non-inferior to IV Iron), if the LCL of the 95% CI for the difference (ferric maltol - IV Iron) in proportions of Hb responders at Week 12 (BOCF) is $\geq -20\%$ for both the ITT analysis and the PP analysis. The p-value in testing the aforementioned hypotheses will be equal to one minus the confidence coefficient corresponding to the CI for the risk difference whose LCL equals -20% (i.e., inverting the CI for the risk difference to a test statistic and calculating the p-value from the test statistic).

The proportion of Hb responders will be summarised for the ITT and PP populations using descriptive statistics by visit over the Treatment Period for each treatment

arm and overall, utilizing all available Hb responder data (i.e., OC approach). Each summary will also present the proportion of Hb responders for the Week 12 visit (MI) using descriptive statistics, and will include the corresponding logistic regression model adjusted difference in the proportions of Hb responders between the two treatment arms, the corresponding adjusted 95% CI for the difference in proportions, and the adjusted p-value from testing the null hypothesis of inferiority in risk difference with non-inferiority margin 20%. Finally, each summary will also present the estimated logistic regression model adjusted odds ratio of Hb responder at Week 12 (MI) between the two treatment arms and corresponding 95% CI for the odds ratio. A bar plot of the Hb responder rate will be presented by visit (OC) and treatment arm for each assessment.

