4 POWER AND SAMPLE SIZE CONSIDERATIONS

This study is designed with a 'responder %' primary endpoint, where responder is a subject who either has at least 2g/dL rise in Hb from baseline or has shift from baseline of anaemic to non-anaemic status. The primary endpoint is the Hb responder rate at Week 12. The comparator group (IV Iron) responder rate is assumed to be 75% and the absolute non-inferiority margin is 20%. The non-inferiority margin is based on clinical opinion, coupled with the fact that in a previous study, the response rate in the placebo arm was less than 5% at 12 weeks.

The study is powered at 90% when the true response rate in the ferric maltol arm is 75% (i.e., the true difference in response rate to IV Iron is 0%). The primary statistical test is based on the 2-sided 95% confidence interval for the difference in response rates between the two treatment groups. This requires 108 subjects per treatment arm. In order to allow for protocol deviations, the sample size has been increased by 12% to 121 subjects per treatment arm.

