6.6 Significance Level

Unless stated otherwise, all statistical tests will be two-sided, with a significance level of 0.05. Confidence intervals (CIs) will be calculated at the 95% level, reflecting a type I error rate of 0.05.

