7.1.2 Non-Date Values

Every effort will be made to obtain required data at each scheduled evaluation from all subjects who have been enrolled. Missing values for the primary efficacy endpoint of Hb responder (i.e., a subject who either has at least 2g/dL rise in Hb from baseline or has shift from baseline of anaemic to non-anaemic status) at Week 12 will be imputed using a Multiple imputation approach for the primary efficacy analysis on the ITT population. If the value of Hb is missing, multiple imputation based on pre-treatment visits will be used in the baseline and multiple imputation based on post-treatment visits will be used to determine the post-baseline value to be used in the primary efficacy endpoint analysis on the ITT population.

As additional sensitivity analyses, missing values for the primary efficacy endpoint on the ITT population will also be imputed using a Last Observation Carried Forward (LOCF) approach up to Week 12.

Missing values for efficacy variables will be replaced for the secondary endpoint analyses, as follows:

- For the key endpoint, 'Hb concentration within normal limits', subjects not returning to a follow-up visit will be assumed to have Hb concentration not within normal limits.
- For the endpoint, 'Increases in Hb concentration of $\geq 1\text{g/dL}$ ', subjects not returning to a follow-up visit will have their Hb concentration imputed using multiple imputation.
- For the endpoint, 'Increases in Hb concentration of $\geq 2\text{g/dL}$ ', subjects not returning to a follow-up visit will have their Hb concentration imputed using multiple imputation.

Missing values for the long-term secondary efficacy endpoints, normalization of Hb at 6 and 12 months and normalization of ferritin at 6 and 12 months, will not be imputed.

Missing values for the SF-36 pharmacoeconomic analysis will be imputed by a LOCF approach up to Week 12. Missing values for all other pharmacoeconomic analyses will be kept as missing.

Safety data will be used according to availability, with no imputation for missing data.

Imputation of data values will only be carried out, where indicated, for computational purposes and fitting of models. Actual data values, as they appear in the original CRFs, will be shown in the data listings.

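### SAP v3.0 multiply imputes missing Week 12 Hb but writes the primary rejection rule on BOCF responders, and sections 7.1.2 and 9.1.1 describe the imputation differently

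*SAP*

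**What the plan says.** Four statements in SAP v3.0 bear on missing Hb in the primary analysis.

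- **Method for Week 12.** Section 9.1.1 says missing responder status in the "primary efficacy analysis will be imputed using a multiple imputation approach for ITT population". Section 7.1.2 agrees, and the results summary described in 9.1.1 labels the Week 12 result MI.
- **Decision rule.** The same section rejects the null if the lower 95% limit for the "difference (ferric maltol - IV Iron) in proportions of Hb responders at Week 12 (BOCF) is" at or above -20%, in both ITT and PP. The only meaning 9.1.1 gives to BOCF is use of the screening value when baseline Hb is missing. BOCF is neither in the abbreviation list nor among the 7.3 definitions. Section 10.1 attaches the same label to post-baseline SF-36 data, for which 7.1.2 specifies LOCF.
- **Week 12 imputation model.** In 7.1.2, "multiple imputation based on post-treatment visits will be used to determine the post-baseline value". In 9.1.1, "Variables considered helpful in guiding this imputation are baseline (Visit 2) Hb concentration and treatment arm", and the PROC MI code has only baseline Hb, arm and Week 12 Hb.
- **Missing baseline.** In 7.1.2, "multiple imputation based on pre-treatment visits will be used in the baseline". In 9.1.1 the screening value is substituted.

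The post-hoc addendum (sections 7 and 9.1.1) restates the rejection rule without the BOCF tag. It imputes by arm from baseline Hb, Week 4 Hb, gender and IBD subgroup, and marks this as a post-hoc change.

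**The concern.** The sentence that decides the trial names a different missing-data rule from the text around it. If baseline Hb is carried forward to Week 12, a subject who was anaemic at baseline has zero change and is a non-responder. Under MI the same subject contributes a predicted Hb. The two rules differ most when the arms lose different proportions of subjects, which is quite possible when an open-label trial compares a daily oral drug with a clinic-administered infusion.

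The two descriptions of the imputation matter separately. A model without Week 4 Hb ignores an early poor response in subjects who then drop out. With the rule unsettled, the choice between readings can be made after the results are known.

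**Working it through.** **Inputs from SAP v3.0**
- Section 6.6: "all statistical tests will be two-sided, with a significance level of 0.05", so the lower 95% limit acts as a one-sided 0.025 test.
- Section 4: "The comparator group (IV Iron) responder rate is assumed to be 75% and the absolute non-inferiority margin is 20"%; "The study is powered at 90% when the true response rate in the ferric maltol arm is 75"%; 108 per arm, raised to 121.
- Section 5.4: subjects with no Week 12 Hb are excluded from PP.
- Section 9.1.1: ITT and PP must both pass.

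**The plan's own sample size**
- n = (1.960 + 1.282)² × 2 × 0.75 × 0.25 / 0.20² = 98.5 per arm.
- With continuity correction: (98.5/4) × [1 + √(1 + 4/(98.5 × 0.20))]² = 108.3, which matches the stated 108.
- 108 × 1.12 = 120.96, or 121.

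The sample size is not in question. The 12% is attributed to protocol deviations. It is not a missing-Hb rate, and the SAP gives none, so every missing proportion below is an assumption.

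**ITT test under each reading**

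Assume 121 per arm, true response 75% in both arms, and missingness unrelated to outcome. An unpooled Wald interval stands in for the plan's adjusted delta-method interval.
- BOCF: rate = 0.75 × (1 - missing), denominator 121.
- MI, approximated by the observed rate: rate = 0.75, denominator 121 × (1 - missing).
- Limit = difference - 1.96 × SE; power = Φ[(difference + 0.20)/SE - 1.96].

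| Missing, ferric maltol / IV iron | BOCF difference | BOCF SE | BOCF limit | BOCF power | MI SE | MI limit | MI power |
|---|---|---|---|---|---|---|---|
| 18% / 6% | 61.5 - 70.5 = -9.0 points | 0.0606 | -20.9% | 44% | 0.0595 | -11.7% | 92% |
| 15% / 9% | 63.75 - 68.25 = -4.5 points | 0.0608 | -16.4% | 72% | 0.0594 | -11.6% | 92% |
| 12% / 12% | 0 | 0.0609 | -11.9% | 91% | 0.0593 | -11.6% | 92% |

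An example in counts: with 12 and 6 subjects missing and 76/109 against 86/115 responders observed, the observed-rate limit is -16.8% (pass). Counting missing as failures gives 76/121 against 86/121 and a limit of -20.1% (fail).

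**Joint rule (ITT and PP)**

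Taking PP as everyone with a Week 12 Hb, simulation gives:
- 75% v 75%, 12% missing in each arm: about 88% joint power with BOCF in ITT, against about 92% with MI.
- 75% v 75%, 6% missing in each arm: about 91% against 94%.
- 55% v 75% (the null boundary), 12% missing in each arm: BOCF-ITT alone passes in about 6% of trials (5.7% by the formula, difference -17.6 points), but ITT and PP together pass in about 2.1%.

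**The two imputation descriptions**

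A patient-level simulation used 300 trials per scenario, an assumed Hb distribution, 20 imputations and the plan's logistic model. It compared MI without Week 4 Hb (9.1.1) with MI using it (one reading of 7.1.2).
- ITT verdicts differed in 2% to 10% of trials when missingness was unrelated to Week 4 Hb, and in 11% to 23% when a poor Week 4 response made missingness more likely.
- In the most unequal of these scenarios (about 19% v 7% missing, true difference 66.4 - 77.2 = -10.8 points) the mean estimate was -8.3 points without Week 4 Hb and -10.8 with it.

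**The case against.** **The tag may be a leftover.** Three places in v3.0 and the SAS code point to MI, and nowhere does v3.0 describe carrying baseline Hb forward to Week 12. This is probably right about intent. But the tag is attached to Week 12 responders, and a confirmatory rejection rule should not have to be inferred.

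**Type I error.** A reader might infer from the 5.7% that BOCF raises the chance of a false non-inferiority claim. The documents do not support that. Both populations must pass and PP omits missing Week 12 Hb, so the joint rate cannot exceed the PP test's own rate. The same applies to fail-to-pass examples in ITT. With 71/106 against 80/106 observed and 15 missing per arm, BOCF-ITT passes (-19.6%), but PP on the observed counts, if there are no other exclusions, fails (-20.6%).

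**The large power loss needs a threefold imbalance in missingness.** This is true. With equal missingness the loss is a few points, and with no missing Week 12 Hb there is none.

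**Parts of the imputation conflict are mild.** Section 7.1.2 does not name Week 4 Hb or sex; Week 4 is the scheduled visit between first dose and Week 12, so it is the natural reading, while adding sex is a modelling recommendation. The 7.3 baseline definition (last pre-dose value) already yields the screening value, so the missing-baseline conflict has an obvious resolution.

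**The addendum drops the tag and adopts a fuller model.** It does, but as a post-hoc change after CSR v1.0. It does not say how the v3.0 rule was applied, and it still refers to v3.0 for data handling.

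**Conclusion.** The contradiction stands. As written, the v3.0 rejection rule does not match the prescribed method, and v3.0 gives two accounts of how Week 12 and baseline Hb are imputed. The conflict between MI and BOCF acts through ITT, and an ITT failure is enough to fail the trial. The cost of a literal reading runs from about 4 points of joint power (12% missing in each arm) to a fall in ITT power from 92% to 44% (18% against 6%). These sizes rest on assumed missingness unrelated to outcome, a 75% response in both arms, and a Wald approximation.

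The harm is mainly a wrongly failed trial, or freedom to choose the rule after seeing data; it is not an excess of false non-inferiority claims. Nor do the documents show that the original analysis used BOCF: they do not say which rule was followed.

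**What to change.** - In 9.1.1, state the rejection rule as Week 12 response with MI for ITT and observed Week 12 Hb for PP. Labelling the whole rule MI would not fit PP.
- Give one imputation model, identical in 7.1.2 and 9.1.1: separately by arm, with baseline Hb, Week 4 Hb, sex and IBD subgroup, as in the addendum.
- Use the 7.3 baseline definition when Visit 2 Hb is missing, and delete the baseline-MI clause in 7.1.2.
- Report missing-equals-non-responder in ITT as a named sensitivity analysis.
- Because CSR v1.0 already exists, rewording v3.0 cannot restore pre-specification. CSR v2 should state which rule the original analysis followed and show the ITT result under both.

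The cost is wording, a few lines of SAS and one extra table, with no new data. The downside is one more sensitivity result, which may be less favourable.
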